1.6 How Study Results Might Impact Future Trials or Practice

This proof-of-principle study is intended to demonstrate that the combination of pembrolizumab with RT has the potential to induce an abscopal response. If results are promising, the question of whether this therapeutic approach enhances anti-tumor activity through an abscopal response can be confirmed in future randomized trials. A future trial in the 2nd-line setting may randomize patients to placebo *vs* placebo plus pembrolizumab *vs* pembrolizumab plus RT.

2. STUDY OBJECTIVES AND ENDPOINTS

2.1 Objectives

2.1.1 Primary Objective

Evaluate the abscopal response rate in CUP patients treated with the combination of pembrolizumab plus radiotherapy.

2.1.2 Secondary Objectives

- Determine the response rate by RECIST 1.1 and informed by irRECIST, of non-irradiated metastatic sites when pembrolizumab is combined with radiotherapy.
- Evaluate treatment-related toxicity.
- Evaluate PFS, OS, TTP, and DCR
- Explore the association between RR and other endpoints (e.g., OS, PFS)

2.1.3 Correlative/Exploratory Objectives

- Evaluate the association of MSI status and mutation load with clinical efficacy
- Evaluate the association of tissue PDL1 expression with clinical efficacy
- Evaluate the association of soluble PD-L1 with clinical efficacy
- Evaluate changes in the CD11a^{high} PD-1^{high} CD8+ T effector population in association with pembrolizumab-based therapy
- Evaluate changes and predictive value of BIM expression in T cells in circulation and the predictive value of BIM/PD-1 expression in tumor infiltrating lymphocytes
- Evaluate the prognostic and predictive value of tumor tissue of origin testing

3. ELIGIBILITY CRITERIA

3.1 Inclusion Criteria

Subject must meet all of the following applicable inclusion criteria to participate in this study:

1. Written informed consent and HIPAA authorization for release of personal health information prior to registration. **NOTE:** HIPAA authorization may be included in the informed consent or obtained separately.
2. Age \geq 18 years at the time of consent.
3. ECOG Performance Status of \leq 2 within 28 days prior to registration.

4. Archival tissue must be available and identified during screening and shipped prior to Day -21. If archival tissue is not available and the subject is not undergoing a standard of care biopsy, the subject must undergo a research biopsy to obtain fresh tissue prior to start of treatment.
5. Carcinoma of unknown primary after the following diagnostic procedures have been performed if clinically indicated and are unrevealing of the primary site:
 - Complete history and clinically appropriate physical
 - CT scan of chest, abdomen, and pelvis
 - Directed evaluation of symptomatic areas
 - Mammogram in women
 - Colonoscopy in patients with liver metastasis or an elevated CEA
 - Direct pathologic comparison with prior tumor specimens, where possible, even if prior tumor is early-stage or clinically remote from current disease

NOTE: Immunohistochemical stains will be performed according to institutional standards. If a primary carcinoma is identified, the patient should undergo treatment as appropriate for that primary tumor and not be enrolled in the study. The above diagnostic workup does not need to be performed if: (1) it was previously completed at the time of original diagnosis or (2) the investigator does not believe the workup has clinical utility at the current time, given that the patient has received interval therapy.

6. Histologic confirmation of metastatic adenocarcinoma, poorly differentiated non-small cell carcinoma, or poorly differentiated squamous carcinoma. **NOTE:** Pathology consultation at Mayo Clinic is recommended if clinically indicated. One scenario is where unknown primary is the most likely diagnosis but immunostains show relatively site-specific marker staining (e.g., CD45, TTF1, chromogranin, GATA3, PAX8, PSA, melanocytic markers). Information provided for pathology consultation should include recent H&P and imaging reports.
7. If and when available, submission of genomic sequencing and expression profiling results is mandatory. Results of testing are not required prior to treatment.
8. At least one measurable lesion (per RECIST 1.1) outside the planned RT fields.
9. Stable or progressive disease after, or was unable to tolerate, at least one line of prior anticancer therapy for this disease. **NOTE:** For patients with stable disease, it is strongly encouraged to confirm the presence of active disease (eg, demonstrating FDG avidity via PET or repeat biopsy).
10. Radiation oncology consultation at enrolling site \leq 56 days prior to registration to confirm at least two metastatic lesions which are targetable by RT at doses and schedule prescribed in this study and which reside in non-overlapping RT fields.

11. Demonstrate adequate organ function as defined in the table below. All screening labs to be obtained within 28 days prior to registration.

System	Laboratory Value
Hematological	
Absolute Neutrophil Count (ANC)	$\geq 900 \text{ K/mm}^3$
Hemoglobin (Hgb)	$\geq 8.5 \text{ g/dL}$ without transfusion or EPO dependency (≤ 7 days prior to assessment)
Platelets	$\geq 90,000 / \text{mcL}$
Renal	
Creatinine OR Calculated creatinine clearance ¹	$\leq 1.5 \times$ upper limit of normal (ULN) OR $\geq 60 \text{ mL/min}$ for subject with creatinine levels $> 1.5 \times$ institutional ULN
Hepatic	
Bilirubin	Total bilirubin $\leq 1.5 \times$ ULN OR Direct bilirubin \leq ULN for subjects with total bilirubin levels $> 1.5 \text{ ULN}$ OR total bilirubin $\leq 2 \times$ ULN if liver metastases are present
Aspartate aminotransferase (AST) and Alanine aminotransferase (ALT)	$\leq 2.5 \times$ ULN OR $\leq 5 \times$ ULN for subjects with liver metastases
Albumin	$> 2.5 \text{ g/dL}$

1 Cockcroft-Gault formula will be used to calculate creatinine clearance (See SPM)

12. Females of childbearing potential must have a negative serum pregnancy test within 72 hours prior to registration. **NOTE:** If the urine test is positive or cannot be confirmed as negative, a serum pregnancy test will be required. **NOTE:** breast milk cannot be stored for future use while the mother is being treated on study

13. Females of childbearing potential and males must be willing to abstain from heterosexual activity (abstinence) or use effective methods of contraception as described in Section 5.5 from the time of informed consent until 120 days after treatment discontinuation.
NOTE: Females are considered of child bearing potential unless they are surgically sterile (have undergone a hysterectomy, bilateral tubal ligation, or bilateral oophorectomy) or they are naturally postmenopausal for at least 12 consecutive months

14. Willingness to return to the enrolling institution for follow up

15. Willingness to provide tissue and blood samples for correlative research purposes

3.2 Exclusion Criteria

Subjects meeting any of the criteria below may not participate in the study:

16. Prior radiation to an area of the body which, if included in the current radiation field, poses an unacceptably high risk of toxicity in the opinion of the investigator. **NOTE:** A prior field that overlaps with the current field, by itself, does not exclude the patient.

17. Any of the following
 - Melanoma. **NOTE:** Positive tumor staining for S-100 or HMB45 alone does not exclude patients.
 - If immunostains are performed, and any of the below tests are positive:
 - Hematologic CD45+ (others such as CD2, CD20, CD30, CD43 also suggest hematologic origin)
 - Lung or thyroid origin (Thyroid Transcription Factor [TTF-1]). **NOTE:** Patients with biopsy proven TTF-1 positive tumor who do not have clinical evidence for either lung or thyroid cancer (e.g. a dominant lung mass) are still eligible.
18. Progressed on 4 or more lines of prior chemotherapy for this cancer. **NOTE:** Bisphosphonates and neoadjuvant/adjuvant anticancer therapies (including locally directed therapies) do not count as a line of therapy with regard to this exclusion criteria.
19. Co-morbid systemic illnesses or other severe concurrent disease which, in the judgment of the investigator, would make the patient inappropriate for entry into this study or interfere significantly with the proper assessment of safety and toxicity of the prescribed regimens.
20. Is currently participating and receiving study therapy or has participated in a study of an investigational agent and received study therapy or used an investigational device within 4 weeks of the first dose of treatment.
21. Has a diagnosis of immunodeficiency or is receiving systemic steroid therapy or any other form of immunosuppressive therapy within 7 days prior to the first dose of trial treatment.
22. Has received prior therapy with an anti-PD-1, anti-PD-L1, or anti-PD-L2 agent.
23. Has a known history of Human Immunodeficiency Virus (HIV) (HIV 1/2 antibodies).
24. Has active autoimmune disease that has required systemic treatment in the past 2 years (i.e. with use of disease modifying agents, corticosteroids or immunosuppressive drugs). Replacement therapy (eg., thyroxine, insulin, or physiologic corticosteroid replacement therapy for adrenal or pituitary insufficiency, etc.) is not considered a form of systemic treatment. **NOTE:** Inhaled steroids or steroid injections for joint disease are allowed.
25. Has known active Hepatitis B (e.g., HBsAg reactive) or Hepatitis C (e.g., HCV RNA [qualitative] is detected).
26. Prior severe allergic reactions to a monoclonal antibody or hypersensitivity to pembrolizumab or any of its excipients.
27. Has had a prior anti-cancer monoclonal antibody (mAb) within 4 weeks prior to study Day 1 or who has not recovered (i.e., \leq Grade 1 or at baseline) from adverse events due to agents administered more than 4 weeks earlier.

28. Other active malignancy which requires current treatment and which in the opinion of the site investigator is likely to interfere with evaluation of disease assessment.
NOTE: Continuation of hormonal therapies is allowed.
29. Has known active central nervous system (CNS) metastases and/or carcinomatous meningitis. Subjects with previously treated brain metastases may participate provided they are stable (without evidence of progression by imaging for at least four weeks prior to the first dose of trial treatment and any neurologic symptoms have returned to baseline), have no evidence of new or enlarging brain metastases, and are not using steroids for at least 7 days prior to trial treatment. This exception does not include carcinomatous meningitis which is excluded regardless of clinical stability.
30. Major surgery \leq 4 weeks from registration. **NOTE:** Diagnostic laparoscopy (without other intervention) and/or biopsies (needle aspirate, core biopsy, open biopsy, etc...) are not considered major surgery. If subject received surgery, they must have recovered adequately from the toxicity and/or complications from the intervention prior to starting therapy.
31. Uncontrolled intercurrent illness which in the opinion of the investigator poses unacceptably high risk when combined with study treatment, including but not limited to the following:
 - Symptomatic congestive heart failure
 - Unstable angina pectoris
 - Severely impaired lung function
 - Known history of active TB (Bacillus Tuberculosis)
 - Uncontrolled diabetes as defined by fasting serum glucose $>1.5 \times$ ULN
(**NOTE:** Optimal glycemic control should be achieved before starting trial therapy.)
 - Significant underlying liver disease such as cirrhosis or severe hepatic impairment
 - Has known psychiatric or substance abuse disorders that would interfere with cooperation with the requirements of the trial.
32. Has an active infection requiring systemic therapy.
33. Has a history or current evidence of any condition, therapy, or laboratory abnormality that might confound the results of the trial, interfere with the subject's participation for the full duration of the trial, or is not in the best interest of the subject to participate, in the opinion of the treating investigator.
34. Is pregnant or breastfeeding, or expecting to conceive or father children within the projected duration of the trial, starting with the pre-screening or screening visit through 120 days after the last dose of trial treatment.

35. For patients in whom planned RT fields will include the heart, any of the following heart conditions, if in the opinion of the investigator they pose unacceptably high risk when combined with study treatment:

- Prior symptomatic congestive heart failure
- Documented myocardial infarction \leq 6 months prior to registration (pretreatment ECG evidence of infarct only will not exclude patients)
- Prior significant ventricular arrhythmia requiring medication
- Prior 2nd or 3rd degree heart block or other types of clinically significant conduction delay \leq 6 months prior to registration
- Clinically significant pericardial disease (including pericardial effusion, pericarditis) or cardiac valvular disease \leq 12 months prior to registration

NOTE: As part of history and physical, all patients must be assessed for signs or symptoms of cardiac disease, or for prior history of cardiac disease. These conditions include but are not limited to diseases related to cardiac valves, pericardium, myocardium, atrioventricular delays or arrhythmias. It is strongly recommended that signs or symptoms of potentially clinically significant disease be evaluated with comprehensive cardiac echo.

36. For patients in whom planned RT fields during the study will include the chest, any of the following, if in the opinion of the site investigator they pose unacceptably high risk when combined with study treatment:

- Prior fistula within thorax, including bronchoalveolar or esophageal.
- Respiratory condition that required oxygen supplementation \leq 3 months prior to registration
- Clinically significant pulmonary hypertension \leq 12 months prior to registration
- Pneumonia requiring treatment \leq 1 month prior to registration
- Pulmonary embolism requiring treatment \leq 6 months prior to registration
- Pleural effusion requiring drainage \leq 12 months prior to registration

37. Has known history of, or any evidence of active, non-infectious pneumonitis

38. Currently uncontrolled hyper/hypothyroidism or hyper/hypocortism if in the opinion of the investigator they pose unacceptably high risk when combined with study treatment

39. Received live vaccine \leq 30 days prior to registration. **NOTE:** Seasonal influenza vaccines for injection are generally inactivated flu vaccines and are allowed; however intranasal influenza vaccines (e.g., Flu-Mist®) are live attenuated vaccines, and are not allowed.

40. History of organ or stem cell transplantation

4. SUBJECT REGISTRATION

All subjects must be registered through HCRN's electronic data capture (EDC) system. A subject is considered registered when an "On Study" date is entered into the EDC system. Subjects must be registered prior to starting protocol therapy.

5. TREATMENT PLAN

5.1 Pre-Medications

There are no pre-medication or hydration requirements for pembrolizumab administration. For radiation therapy please use institutional standards for pre-medications.

5.2.1 Pembrolizumab

Pembrolizumab 200 mg will be administered as a 30 minute IV infusion. Sites should make every effort to target infusion timing to be as close to 30 minutes as possible. However, given the variability of infusion pumps from site to site, a window of -5 minutes and +10 minutes is permitted (i.e., infusion time is 30 minutes: -5 min/+10 min). Additional information can be found in the pharmacy manual.

A window of \pm 3 days may be applied to all study visits to accommodate observed holidays, inclement weather, scheduling conflicts etc. Date and time of each drug administration should be clearly documented in subject's chart and electronic case report forms (eCRFs). After the completion of the period of concurrent RT, pembrolizumab monotherapy may be given up to \pm 7 days of the scheduled dose on Day 1 of each cycle. All trial treatments are administered on an outpatient basis.

NOTE: Dosing of pembrolizumab may be withheld in the case of medical/surgical events or logistical reasons (i.e. elective surgery, unrelated medical events, subject vacation, holidays) not related to study therapy. Patients should be placed back on study therapy within 3 weeks of the scheduled interruption to remain aligned with the Q3W dosing interval. The reason for withholding dosing of either pembrolizumab should be documented in the subject's study record.

5.2.2 Radiation Therapy

Palliative external beam radiation therapy is administered to 2 separate non-overlapping sites of metastatic disease. Radiation therapy is administered to the 1st site of metastatic disease on Days 1-5 of Cycle 1 and to the 2nd site of metastatic disease on Days 1-5 of Cycle 2. Here are guidelines for treatment:

- The treating radiation oncologist will select sites to be treated with radiotherapy with preference given to locations that are currently symptomatic or may become symptomatic if there is local tumor progression. Lesions that may provide palliative benefit may also be selected.
- The entire lesion does not need to be completely encompassed within the radiation field.
- If there are > 2 candidate metastatic sites, the treating radiation oncologist should consider treating sites with lower risk of treatment related adverse effects. No more than 2 metastatic sites may be treated.
- A third measurable lesion located outside the planned RT fields must NOT be radiated.

5.2.2.1 Dose specifications and technical factors

The trial administers a total dose of 20, 25, or 30 Gy over 5 fractions per metastatic lesion. The treating radiation oncologist may select the prescription dose to meet the tumor coverage requirements and the organ at risk constraints (OAR) as specified below. It is recommended that the highest dose possible be administered, so long as all mandatory organs at risk (OAR) criteria are met. General recommendations for dose based on lesion site are described below.

Total dose (Gy)	Fractions	Dose per fraction	Example sites
20-30	5	4-6	Liver, lung, bone (non-spine)
20-25	5	4-5	Abdomen/pelvis
20	5	4	Spine

Dose should be prescribed such that $\geq 95\%$ of the PTV receives the prescription dose. All mandatory OAR criteria must be met at a given radiotherapy dose level, or else the dose must be lowered to the next lowest dose level.

The energy of the treatment beam will be at least 6 MV and no greater than 18 MV. The use of intensity-modulated radiation therapy (IMRT) is allowed, however, proton beam radiation therapy and intraoperative radiotherapy (IORT) are NOT allowed. Radiation dose prescriptions will be calculated using heterogeneity corrections to take into account tissue inhomogeneities in treatment planning.

5.2.2.2 Immobilization and Simulation

After study enrollment, patients will undergo CT simulation. All patients will undergo high-resolution CT-based (≤ 2 mm slices) 3D treatment planning in custom made immobilization devices. IV contrast and other contrast agents can be used at physician's discretion and as per standard of care. Respiratory motion can be assessed and managed when clinically indicated (i.e. lung, liver, and adrenal gland metastases) with a 4D CT scan. Respiratory gating techniques (including breath hold techniques) may be employed for sites with tumor motion greater than 1 cm.

5.2.2.3 Treatment Planning and Target Volumes

When available, the RT planning process can incorporate diagnostic image fusion (MRI, PET/CT) with planning CT as needed to delineate the target volume and OAR. Gross tumor volume (GTV) will cover the entire metastasis to be treated. For metastases prone to respiratory motion, an internal target volume (ITV) may be generated based on the 4D CT images. Clinical target volume (CTV) expansion will be 5 mm on the GTV or ITV. For spinal lesions, the entire involved vertebra(e) should be included in the CTV. The CTV may be modified to exclude overlap with uninvolved adjacent OAR. The PTV will be a 5 mm uniform expansion of the CTV.

5.2.2.4 Treatment Delivery

Daily verification of the treatment setup will be performed with kilovoltage x-ray (2D) images or volumetric (3D) imaging (kilovoltage or megavoltage CT). CT volumetric imaging (3D to 3D match) is recommended for lung, liver, soft tissue and lymph nodes metastases. For bone metastases, a pair of kV orthogonal (2D) imaging can be used. RT treatments will be delivered on consecutive weekdays. RT treatments can be delivered on weekends and holidays but is not required.

5.2.2.5 Radiation Compliance Criteria

Target coverage

PTV: $D95 \geq 95\%$ and max dose (0.03 cc) $\leq 120\%$ (while hotspots in GTV is encouraged, hotspots in PTV should be avoided where it overlaps with organs at risk.)

Organs at risk

All mandatory organs at risk (OAR) constraints must be met for treatment on this protocol. If these constraints cannot be met at a given total dose, then the dose must be lowered (Lowest dose is 20 Gy in 5 fractions). For example, if the mandatory constraints cannot be met at a prescription dose of 30 Gy in 5 fractions, then the dose must be lowered to 25 Gy in 5 fractions. Questions regarding radiation planning can be directed to [name] ([contact]) or [name] ([contact]).

Mandatory OAR

Optic chiasm: $D0.03\text{cc}[Gy] < 23\text{ Gy}$
Optic nerves: $D0.03\text{cc}[Gy] < 23\text{ Gy}$
Cochlea: $D0.03\text{cc}[Gy] < 23\text{ Gy}$
Brainstem: $D0.03[Gy] < 23\text{ Gy}$
Spinal cord: $D0.03[Gy] < 23\text{ Gy}$
Cauda equina: $D0.03[Gy] < 28\text{ Gy}$
Brachial plexus: $D0.03[Gy] < 28\text{ Gy}$
Sacral plexus: $D0.03[Gy] < 28\text{ Gy}$
Esophagus: $D0.03[Gy] < 28\text{ Gy}$
Trachea: $D0.03[Gy] < 33\text{ Gy}$
Proximal bronchial tree: $D0.03[Gy] < 33\text{ Gy}$
Heart: $D0.03[Gy] < 33\text{ Gy}$
Stomach: $D0.03[Gy] < 28\text{ Gy}$
Duodenum: $D0.03[Gy] < 28\text{ Gy}$

Small bowel: D0.03[Gy] < 28 Gy
Large bowel: D0.03[Gy] < 28 Gy
Rectum: D0.03[Gy] < 33 Gy
Bladder: D0.03[Gy] < 33 Gy
Skin: D0.03[Gy] < 33 Gy
Lung: V20 < 10%
Liver: CV21Gy[cc] > 700 cc
Kidney total: V12.5Gy[%] < 67 %, Mean[Gy] < 12.5 Gy

Recommended (but not required) OAR

Esophagus: V19.5Gy[cc] < 5 cc
Trachea: V16.5Gy[cc] < 4 cc
Proximal bronchial tree: V16.5Gy[cc] < 4 cc
Stomach: V18Gy[cc] < 10 cc
Duodenum: V18Gy[cc] < 5 cc, V12.5Gy[cc] < 10 cc
Small bowel: V19.5Gy[cc] < 5 cc
Large bowel: V25Gy[cc] < 20 cc
Rectum: V25Gy[cc] < 20 cc
Bladder: V18.3Gy[cc] < 15 cc
Femoral heads: V30Gy[cc] < 10 cc

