- Monitoring will include late lung toxicities, given that pneumonitis often does not appear until several months after radiation treatment is completed.

Radiation-Induced Liver Disease (RILD) usually develops 1-2 months after RT and describes a clinical syndrome composed of fatigue, ascites, elevated LFTs and abdominal pain. Emami et al ([Emami et al., 1991](#)) estimated the acceptable liver tolerance dose (TD5/5; tolerance dose that may cause 5% complication rate within 5 years) of 3000, 3500, and 5000 cGy when whole, 2/3, and 1/3 of the liver was radiated, respectively. This task force estimation is limited by the 2D treatment technique employed at the time. The Quantitative Analysis of Normal Tissue Effects in the Clinic (QUANTEC) ([Marks et al., 2010](#)) provides the more recent guidelines using the 3D dose/volume/outcome data. In this analysis, preexisting liver dysfunction (Child-Pugh B or C), mean liver dose and V30 (volume receiving 30 Gy or higher) were associated with RILD ([Pan et al., 2010](#)). Accordingly, patients with primary liver tumors have a lower radiation dose/volume threshold for developing RILD than patients with liver metastases. RILD data for partial liver radiation has been studied using the Lyman-Kutcher-Burman model by the investigators at the University of Michigan ([Dawson et al., 2002](#)). In this study, the rate of RILD grade 3 or higher within 4 months in 203 patients treated with 3D conformal radiation and concurrent hepatic arterial chemotherapy were analyzed. Although some patients received 90 Gy, no RILD was noted when the mean liver dose was <31 Gy. Therefore, in the current study, we will use the following liver constraints as described in QUANTEC to minimize liver toxicity: mean liver <= 30 Gy and >=700 ml of normal liver to receive <=15 Gy (which is a stricter constraint used for 5 fraction SBRT regimen).

The safety and tolerability of lung/liver RT in combination of pembrolizumab has not been extensively examined and, with the implementation of appropriate safeguards (see below: Eligibility, Study Design), is a focus of the current trial. The combination of pembrolizumab + concurrent radio(chemo)therapy is being examined in multiple trials in other tumor types:

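### The rationale promises at least 700 ml of normal liver at no more than 15 Gy, but the mandatory organ-at-risk list uses 21 Gy, so the promised limit is not enforced

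*Combined protocol and SAP*

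**What the plan says.** Section 1.4.2 discusses radiation-induced liver disease (RILD) and then makes a commitment for this trial: "in the current study, we will use the following liver constraints as described in QUANTEC to minimize liver toxicity". The constraints are "mean liver <= 30 Gy and >=700 ml of normal liver to receive <=15 Gy". The second is described as one "which is a stricter constraint used for 5 fraction SBRT regimen". The same section concedes: "The safety and tolerability of lung/liver RT in combination of pembrolizumab has not been extensively examined".

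The operative rules are in Section 5.2.2. Section 5.2.2.1 allows 20, 25 or 30 Gy in 5 fractions per lesion and gives liver as an example site for the full range. It recommends the highest dose that meets the mandatory organ-at-risk (OAR) criteria, and states: "All mandatory OAR criteria must be met at a given radiotherapy dose level, or else the dose must be lowered". Section 5.2.2.5 makes the mandatory list a condition of treatment on protocol and names 20 Gy as the lowest dose. The only liver entry in that list is "Liver: CV21Gy[cc] > 700 cc". The list of recommended constraints has no liver entry. Neither limit from Section 1.4.2 appears anywhere in Section 5.2.2.

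**The concern.** The two sections give different dose thresholds for the same 700 cc of liver. A difference in fractionation does not explain this: Section 1.4.2 ties its figure to a 5-fraction regimen, and the trial treats in 5 fractions. The Section 1.4.2 text is also more than background, because it says what this study will do to limit liver toxicity.

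Sites plan against the mandatory list. From 30 or 25 Gy, the list decides whether the dose must come down. At 20 Gy, where there is no lower level, it decides only whether the patient can be treated on protocol. If the list is looser than the rationale, a plan can be fully compliant while breaching the limit that anyone reading the rationale would believe is in force. The combination under study is one the protocol itself describes as not extensively examined.

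**Working it through.** **Inputs.** From Section 1.4.2: at least 700 ml at or below 15 Gy, and mean at or below 30 Gy. From Section 5.2.2.5: `CV21Gy` above 700 cc, and a PTV maximum of 120% of prescription. From Section 5.2.2.1: 20, 25 or 30 Gy in 5 fractions.

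**Assumptions.** (a) `CV21Gy` is not defined. It is read as the volume receiving less than 21 Gy, since a lower bound on volume protects an organ only on that reading. (b) Both limits are taken on the same dose basis, one course. (c) No liver receives more than the PTV maximum.

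**Step 1: thresholds against prescription.** The gap is 21 − 15 = 6 Gy, and 21/15 = 1.4.

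| Prescription | 15 Gy as share | 21 Gy as share | 120% cap |
|---|---|---|---|
| 30 Gy | 15/30 = 50% | 21/30 = 70% | 36 Gy |
| 25 Gy | 15/25 = 60% | 21/25 = 84% | 30 Gy |
| 20 Gy | 15/20 = 75% | 21/20 = 105% | 24 Gy |

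At 20 Gy the mandatory threshold lies above the prescribed dose. Liver inside the PTV at exactly 20 Gy counts towards the spared 700 cc, and only hot spots from 21 to 24 Gy count against it. That liver does not count towards 700 ml at or below 15 Gy.

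**Step 2: direction.** Liver at or below 15 Gy is a subset of liver below 21 Gy. Meeting the Section 1.4.2 volume limit therefore implies meeting the Section 5.2.2.5 line, apart from the case of exactly 700 cc (at least 700 in one, more than 700 in the other). The reverse does not follow.

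**Step 3: an example at 30 or 25 Gy, with assumed volumes.** Take 600 cc at or below 15 Gy, 200 cc between 15 and 21 Gy, and 400 cc at or above 21 Gy, for a total of 1200 cc.

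- Mandatory list: 600 + 200 = 800 cc below 21 Gy. 800 > 700, so it passes.
- Rationale: 600 cc at or below 15 Gy. 700 − 600 = 100 cc short, so it fails.
- Upper bound on mean dose at 30 Gy: (600×15 + 200×21 + 400×36)/1200 = 27,600/1200 = 23.0 Gy, below 30 Gy.

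Only the volume limit is breached. The 400 cc band leaves room for target coverage, since 95% of prescription is 28.5 Gy or 23.75 Gy.

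**Step 4: when the verdicts differ.** Let V be the volume at or below 15 Gy and m the volume between 15 and 21 Gy. The sections disagree when V < 700 and V + m > 700, that is, 700 − m < V < 700. For assumed m of 50, 100 and 200 cc, the window for V is 650–700, 600–700 and 500–700 cc.

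**Step 5: the mean-dose limit.** It is also missing from the list, but in a single course it seldom matters. At 20 and 25 Gy the caps are 24 and 30 Gy, so a mean above 30 Gy is impossible. At 30 Gy, take the extreme of 700 cc at 21 Gy and all other liver at 36 Gy. The mean exceeds 30 Gy only if 700×21 + (L − 700)×36 > 30L, which gives a total liver volume L > 700×15/6 = 1750 cc.

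**The case against.** The strongest reply is that the operative text is not in doubt. Sites have one binding liver rule, and the conflict is between a rationale section and a treatment section. Section 1.4.2 also refers to safeguards in the eligibility and design sections, and the protocol contains several: bilirubin, transaminase and albumin limits (3.1), exclusion of cirrhosis or severe hepatic impairment (3.2), a preference for lower-risk sites when more than two are candidates (5.2.2), chemistry panels at each cycle (Section 7), and hepatic toxicity rules (6.1 and 6.2). The prescription range and the 120% cap bound liver dose as well. Section 1.4.2 reports of its cited cohort that "no RILD was noted when the mean liver dose was <31 Gy". Finally, the example volumes are assumed, and the direction of the gap rests on undefined notation.

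Much of this stands as a limit on the consequence. It does not remove the conflict. The other protections do not put the 15 Gy limit into force. The cited cohort received hepatic arterial chemotherapy, not pembrolizumab, and its fractionation is not stated. The lung figures show a different pattern: Section 1.4.2 expects V20 below 20% and the mandatory list requires below 10%, so there the operative rule is tighter than the rationale. The 15 and 21 Gy figures differ on any reading of the notation; only the direction depends on the reading taken here.

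One point deserves weight. If one limit were meant per course and the other for the sum of two hepatic courses, the subset argument in Step 2 could fail. The protocol requires non-overlapping fields but does not exclude two liver sites, and does not say which dose basis applies.

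**Conclusion.** The concern holds: the protocol contradicts itself on the liver volume-dose limit, and the limit stated in the rationale is absent from the list that governs treatment. On the reading of `CV21Gy` as volume below 21 Gy, and with both limits on the same single-course basis, the enforced threshold is 6 Gy higher at every prescription level. At 20 Gy it exceeds the prescription itself.

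The practical size is uncertain. Disagreement is confined to plans whose liver volume at or below 15 Gy falls short of 700 cc by less than the volume lying between 15 and 21 Gy. The documents do not show how many plans would fall there. This is a radiation-safety inconsistency that should be corrected. The primary endpoint, sample size and error rates are not affected.

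**What to change.** The sponsor's radiation oncology leads should reconcile Sections 1.4.2 and 5.2.2.5 so that both state the same liver volume-dose constraint, and should define `CV21Gy` or whatever replaces it. Which figure is right is for them to decide.

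Three further details can be settled in the same text:

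- whether the constraint refers to liver or to normal liver, which at 20 Gy affects what inside the PTV counts as spared;
- whether the mean-dose limit applies;
- whether limits apply to each course or to the sum when both irradiated sites are hepatic.

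The cost is one amendment with one required decision and one definition. There is no statistical cost.
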